### **3.1 STUDY DESIGN**

This study is a 2 arm randomized clinical trial involving diagnosed knee osteoarthritis patients who are eligible to the study from February 2015 to July 2015 at Hospital Putrajaya and Hospital Serdang, Selangor, Malaysia, will be conducted. The sample population will be randomly divided into experimental and control groups by applying block randomization technique in a ratio 1:1. Random allocation will consider and eliminate the possible bias based on the socio- demographic characteristics of the patients. The experimental group will receive Cognitive Behavioral Treatment (CBT) provided with The Knee Book (Ministry of Health, 2013) added to standard routine care, whereas the control group will receive standard routine care only provided with The Knee Book and follow the same schedule of assessment as the experimental group. For standard routine care, patients need to attend their clinic and physiotherapy session as usual based on their fixed appointment date. A baseline measurement on patients' knee pain intensity, functional disability, psychological distress (depression, anxiety and stress), fear- avoidance beliefs, pain catastrophising and self- efficacy in pain management will be collected on respondents in both intervention and control group prior to the introduction of CBT. The efficacy endpoint will then be measured immediately, one month and six months after intervention. Figure 3.1 shows the schematic diagram of the study design.

[figure not shown]

Figure 3 Schematic diagram of the study design

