### 3.5 SAMPLE SIZE ESTIMATION

The formula for calculating sample size in hypothesis testing by comparing means will be used (Lameshow et al., 1990):

$$n = \frac{2\bar{\delta}^2[Z_{1-\alpha/2} + Z_{1-\beta}]^2}{(\mu_1 - \mu_2)^2} \quad (\text{For continuous variable})$$

Where:

(a) Using an assumed expected outcome of **knee pain intensity decrease** within 6 months of therapy,

$\bar{\delta}$  = estimated standard deviation (assumed to be equal for each group) is 10.85 (Wideman et al., 2014)

$\mu_1$  = estimated mean knee pain score for at least 6 months is 16.54

$\mu_2$  = estimated mean baseline knee pain score is 20.68 (Wideman et al., 2014)

$Z_{1-\alpha/2}$  = standard error when  $\alpha = 0.05$  (95% Confidence Interval) = 1.96

$Z_{1-\beta}$  = standard error associated with power = 0.842 ( $\beta = 0.20$ )

Power ( $1-\beta$ ) = 80%

Effect size ( $ES\mu$ ) =  $\mu_1 - \mu_2 / \bar{\delta}$  where  $\bar{\delta}$  = pooled standard deviation =  $\sqrt{\delta_1 + \delta_2} / 2$

$ES\mu = 0.38$  which corresponds to  $n = 109$

Based on the above formula, the required minimum sample size for each group,  $n$  is **109**. To factor in 20% attrition, total required per group will be **131**; hence a total of **262** patients will be required for the sample in both groups.

(b) Using an assumed expected outcome of **functional disability decrease** within 6 months of therapy,

$\bar{\delta}$  = estimated standard deviation (assumed to be equal for each group) is 35.61 (Wideman et al., 2014)

$\mu_1$  = estimated mean functional disability score for at least 6 months is 59.50

$\mu_2$  = estimated mean baseline functional disability score is 74.38 (Wideman et al., 2014)

$Z_{1-\alpha/2}$  = standard error when  $\alpha = 0.05$  (95% Confidence Interval) = 1.96

$Z_{1-\beta}$  = standard error associated with power = 0.842 ( $\beta = 0.20$ )

Power ( $1-\beta$ ) = 80%

Effect size ( $ES\mu$ ) =  $\mu_1 - \mu_2 / \bar{\delta}$  where  $\bar{\delta}$  = pooled standard deviation =  $\sqrt{\delta_1 + \delta_2} / 2$

$ES\mu = 0.42$  which corresponds to  $n = 90$

Based on the above formula, the required minimum sample size for each group, n is **90**. To factor in 20% attrition, total required per group will be **108**; hence a total of **216** patients will be required for the sample in both groups.

(c) Using an assumed expected outcome of **depression level decrease** within 6 months of therapy,

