Based on the above formula, the required minimum sample size for each group,  $n$  is **73**. To factor in 20% attrition, total required per group will be **88**; hence a total of **176** patients will be required for the sample in both groups.

From the sample size estimation of the outcomes, the outcome measure of **knee pain intensity decrease** provides the **largest sample size (n = 131 per group)**, and this will be used as the sample size for this research study.

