### **3.13 DATA ANALYSIS PLAN**

Data collected will be analyzed using Statistical Package for Social Sciences software (SPSS) version 21. Parametric tests (T-test, repeated measures ANOVA and correlation analysis) will be performed. P value for test of significance of results will be set at 0.05, alpha level (Type 1 error) at 0.05 (Confidence Interval of 95%). Analysis of outcomes will be by intention-to-treat where all participants who were randomized and entered the trial need to be included in the analysis in the condition to which they were assigned, regardless of whether they completed the trial, or may even have switched over to receive the incorrect treatment, per-protocol (complete case) analysis and chi square test.

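### Attrition is added as n × 1.2 rather than n ÷ 0.8, so 131 per arm leaves about 105 after 20% loss, below the required 109

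*Protocol*

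**What the plan says.** Section 3.5 of the protocol sizes the trial seven times, once per outcome, with the standard two-mean formula. For knee pain intensity it reaches a minimum of 109 per group and goes on: "To factor in 20% attrition, total required per group will be" 131, giving 262 overall. At the end of 3.5 this is named as the "largest sample size (n = 131 per group") and adopted for the study. Allocation is "by applying block randomization technique in a ratio 1:1" (3.1).

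Three other statements bear on the point:

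- Section 3.8 (Procedures) says that withdrawn participants are not replaced.
- Section 3.8 (Randomization and Masking) selects 300 names and allocates them to the two arms. It gives no derivation of 300.
- Section 3.13 plans an intention-to-treat analysis and also a per-protocol, complete-case analysis.

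**The concern.** An attrition allowance exists to leave the required number of patients after the expected loss. Attrition of 20% means a fifth of those enrolled are lost, so enrolment has to be the required number divided by 0.80. Adding 20% of the required number falls short, because the loss is then taken from the larger, inflated total.

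The error reaches the figure the protocol adopts as its sample size. Knee pain has the largest requirement of the seven outcomes, so no other outcome supplies slack. With no replacement of withdrawals, nothing in 3.5 makes up the difference. At stake is whether the stated 80% power for the primary outcome is met under the protocol's own attrition assumption.

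**Working it through.** **Inputs for knee pain (section 3.5 unless noted)**

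- SD: "estimated standard deviation (assumed to be equal for each group) is 10.85"
- Mean at six months: "estimated mean knee pain score for at least 6 months is 16.54"
- Mean at baseline: "estimated mean baseline knee pain score is 20.68"
- Two-sided α = 0.05, Z = 1.96 (also set in 3.13: "alpha level (Type 1 error) at 0.05 (Confidence Interval of 95"%)
- Power 80%: "standard error associated with power = 0.842"
- Attrition 20%

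**Step 1: reproduce 109.** The formula is n = 2σ²(Z₁₋α/₂ + Z₁₋β)² ÷ (μ₁ − μ₂)².

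- Difference: 20.68 − 16.54 = 4.14. Effect size: 4.14 ÷ 10.85 = 0.3816, stated as 0.38.
- Unrounded inputs: 2 × (10.85 × 2.802 ÷ 4.14)² = 107.85, so 108.
- Rounded effect size: 2 × (2.802 ÷ 0.38)² = 108.74, so 109.

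The stated 109 is reproduced with the rounded effect size.

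**Step 2: reproduce 131.** 109 × 1.2 = 130.8, so 131. The plan's figure is therefore n × (1 + 0.20).

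**Step 3: apply the loss.**

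- 131 × 0.80 = 104.8, about 4 below 109 and also below 108.
- Loss that 131 can absorb while keeping 109: 1 − 109 ÷ 131 = 16.8%, not 20%.
- Enrolment that keeps 109: 109 ÷ 0.80 = 136.25, so 137 per arm and 274 in total. That is 6 more per arm and 12 more overall.

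**Step 4: power, using the plan's SD and difference.** Under the normal approximation, power = Φ(0.3816 × √(n ÷ 2) − 1.96).

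| Completers per arm | Normal approximation | Two-sample t |
|---|---|---|
| 109 (the plan's minimum) | 80.4% | 80.1% |
| 105 | 79.0% | 78.6% |
| 104 | 78.6% | 78.2% |
| 120 (150 per arm less 20%) | 84.0% | 83.7% |

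**Step 5: the other outcomes.** The same rule is used throughout.

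| Outcome | Minimum n | Stated | Stated × 0.80 | Minimum ÷ 0.80, rounded up |
|---|---|---|---|---|
| Knee pain | 109 | 131 | 104.8 | 137 |
| Functional disability | 90 | 108 | 86.4 | 113 |
| Depression | 92 | 111 | 88.8 | 115 |
| Anxiety | 74 | 89 | 71.2 | 93 |
| Fear-avoidance | 77 | 93 | 74.4 | 97 |
| Catastrophising | 68 | 82 | 65.6 | 85 |
| Self-efficacy | 73 | 88 | 70.4 | 92 |

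Every stated figure falls below its own minimum after 20% loss.

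**The case against.** Multiplying by 1.2 is a common shortcut, and its cost here is slight. Under the plan's own normal-approximation formula, power drops to about 79%, a change smaller than the uncertainty in the assumed SD, effect and attrition. That is fair, and it limits the weight of the point. It does not make 131 sufficient for the purpose the protocol gives it.

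The stronger objection is that the shortfall may never occur. Section 3.8 allocates 300 names, so 150 per arm at 1:1, which leaves 150 × 0.80 = 120 and power of about 84%. If 300 is the true target, the trial is adequately sized on these inputs. However, 300 is not derived or linked to attrition, and it conflicts with the 131 that 3.5 says will be used. Section 3.8 also describes 13 subgroups of eight to ten in each arm, which is 13 × 8 = 104 to 13 × 10 = 130 per arm and cannot hold 150. The document does not settle which number governs.

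Two smaller points stand:

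- The figure 137 follows from keeping the stated 109. From the unrounded inputs, 108 ÷ 0.80 = 135 per arm, 270 in total. The shortfall remains either way.
- Correcting the six secondary calculations changes nothing operationally, since about 105 completers per arm exceeds each of their minimums (the largest is 92).

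Finally, the formula's two means are a baseline and a six-month value, not two arm means. The powers above are therefore conditional on the plan's inputs and do not endorse them.

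**Conclusion.** The concern holds: the sample size adopted in 3.5 is wrong as written. With 131 per arm and the stated 20% loss, about 105 remain against a required 109. That is a gap of about 4 completers per arm, or 6 in enrolment, and power is about 78–79% rather than 80%. This takes the protocol's SD, difference, α and attrition as given and assumes lost patients contribute no six-month score. Intention-to-treat inclusion does not by itself supply that missing score. The shortfall applies to the 131 per arm in 3.5 and would not arise if 300 were randomised as 3.8 describes.

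**What to change.** In section 3.5, replace 131 per group and 262 in total with 137 and 274 (109 ÷ 0.80). For consistency, change items (b) to (g) from 108, 111, 89, 93, 82 and 88 to 113, 115, 93, 97, 85 and 92, and correct their totals. Alternatively, keep 131 and state that power is about 79% after 20% loss, conditional on the inputs given.

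Either way, state one enrolment target and make 3.5, the 300 names in 3.8 and the subgroup count in 3.8 agree with it. The cost is corrected text. If 300 is the true target, no further recruitment is needed. If 262 was the target, it is 12 more patients.

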### **3.6 SAMPLING FRAME**

A list of all patients with knee osteoarthritis seen at orthopaedic clinic of each recruitment site (obtained from the medical records department of each hospital).

### **3.7 SAMPLING UNIT**

Individual patients who are diagnosed with knee osteoarthritis, assessed and found to be eligible to the study based on medical examination and radiographic evidence criteria.

### **3.8 SAMPLING METHOD**

#### **Randomization and Masking**

The participants will be recruited from Hospital Putrajaya and Hospital Serdang. Participants will be identified from physician and from searches of patient records

that had consulted for knee pain problem within the period of February 2015 to July 2015. Patients will be invited to give consent to be contacted by staff nurse for the permission to review patients' medical records for a diagnosis of knee osteoarthritis. Patients of each recruitment site who were eligible will be contacted by researcher to enquire their willingness to participate in this research study. Potentially eligible patients will be invited to attend a face-to-face appointment with a researcher to discuss participating in the trial and to confirm their eligibility. Ineligible patients (and those who declined participation) will be referred back to their general practitioner. Those eligible patients who agreed to participate in this study will be in a list and numbered. The number in the name list of all eligible knee osteoarthritis patients who were agreed for the participation will be randomly chosen by using draw logs until 300 names been obtained from the list, in order to ensure that no bias will be involved in patient recruitment.

The selected 300 names from the sampling frame will be randomly allocated to either of the experimental or control group based on block randomization method by using random allocation software after the written consent obtained and baseline questionnaire administered. Then, the names will be divided into 13 smaller subgroups (eight to ten each subgroup) in each intervention and placebo group. All the names in the subgroups will be contacted personally before every assignment by a hospital staff who will be blinded to group allocation.

Because of the nature of the treatments, the participants or those providing the interventions to treatment assignment will be unable to mask. However, research assistants who obtained and assessed outcomes will be masked to assignment. Besides, the research assistants for treatment and control group are different. The research assistants then will submit the outcome measurements at each time measure to the researcher who is undertaking the analysis task.

The full written informed consent will be obtained from patients at least seven days before the intervention start at waiting area of orthopedic clinic. They will be contacted personally by the hospital staff.

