### 3.11 INTERVENTION PROTOCOL

Both the intervention and control group will receive standard routine care throughout the study. They have to attend clinic and physiotherapy session as usual on their fixed appointment date. However, the control group will be provided with The Knee Book (Ministry of Health, 2013) and not receive further intervention. Patients in the intervention group will be provided with The Knee Book (Ministry of Health, 2013) and to receive a three sessions of group Cognitive Behavioral Therapy (CBT) (each session will be last for two and a half hour) bi- weekly. The session will be held in a group of eight to ten patients and supervised by an experienced senior clinical psychologist ([name]) and a physiotherapist. The intervention will be delivered by physiotherapists and nurses who will receive at least one day of training specific to the trial from an experienced senior clinical psychologist with CBT experience. Each session will be audio- recorded with a written consent from the patients. Fidelity of the CBT session will be assessed for a random sample of recordings by the experienced psychologist with the Cognitive Therapy Rating Scale (Blackburn et al., 2000), which is a valid and reliable CBT rating scale. It has high internal reliability which is cronbach alpha 0.95 and good face validity. In addition, patients in the intervention group will assess the Client Satisfaction Questionnaire (CSQ-8) after the last session of group CBT received for measuring satisfaction with the therapy provided (Attkisson, 2012). It has high coefficient alpha (ranged from 0.83 to 0.93).

The outline of the Cognitive Behavioral Therapy module is prepared and modified based on Linton (2005). The CBT intervention will include an introduction, lecture (knowledge and insight), problem solving, skills training, homework assignments and a feedback of the session. An example of a knee OA patient will be applied throughout the intervention as a model for discussion and practice in problem solving, in order to enhance peer support and social bonding. Compliance with CBT is defined as attendance at the initial assessment and at least three subsequent sessions.

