### 3.19 BUDGET

Budget details	Amount requested			
	Year 1 (RM)	Year 2 (RM)	Year 3 (RM)	Total (RM)
Salary and wages (1 Hospital-based research assistant and 1 Graduate Research Assistant)	NIL	6,000	NIL	6,000
Travelling and Transportation/ (Transportation costs to-and-from study site)	NIL	1,000	NIL	1,000
Rental	NIL	NIL	NIL	NIL
Research Materials & Supplies (Printing of Questionnaires, forms etc)	500	1,000	500	2,000
Maintenance and Minor Repair	NIL	NIL	NIL	NIL
Professional Services	NIL	2,000	NIL	2,000
Accessories and Equipment	NIL	NIL	NIL	NIL
TOTAL AMOUNT (RM)	500	10,000	500	11,000

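### Outcome collectors are called masked but differ by arm: the masking is unlikely to hold, and assistant differences at follow-up cannot be separated from the CBT effect

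*Protocol*

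**What the plan says.** Section 3.8 of the Protocol, under Randomization and Masking, first accepts that "the participants or those providing the interventions to treatment assignment will be unable to mask". Three consecutive sentences on the research assistants follow:

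- The first claims masking for those who collect the outcomes: "However, research assistants who obtained and assessed outcomes will be masked to assignment".
- The second separates these staff by arm: "Besides, the research assistants for treatment and control group are different".
- The third has the same staff pass the results of each assessment to the person who does the analysis.

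Other parts of the Protocol that bear on this:

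- Section 3.11 gives delivery of CBT to other staff: "The intervention will be delivered by physiotherapists and nurses who will receive at least one day of training".
- Section 3.8 places allocation "after the written consent obtained and baseline questionnaire administered", so baseline data precede any split by arm.
- Section 3.12 makes the data collection tool a self-administered questionnaire, with follow-up immediately, one month and six months after the intervention.
- Section 3.19 budgets "1 Hospital-based research assistant and 1 Graduate Research Assistant" and does not assign either post to an arm, a hospital or a task.

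**The concern.** The first two sentences on the assistants pull against each other. The first claims masking. The second sets up staffing that needs the allocation in order to work, because someone must know a patient's arm to choose the assistant. The protocol describes no step that would keep the assistants unaware of which list they hold.

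Two things are at stake. The first is the credibility of the masking statement. Participants are unmasked and one arm attends group sessions. When an assistant sees one arm only, a single remark about those sessions discloses the arm of all that assistant's patients, not of one patient.

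The second is confounding, which would remain even if every assistant stayed unaware. If one set of assistants prompts more, checks forms for gaps more carefully or pursues late questionnaires harder, that difference falls entirely between the arms. It could affect the primary outcome (knee pain intensity) and every secondary outcome at all three follow-ups. It could also affect who is still in the analysis, in a trial that allows for 20% attrition.

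**Working it through.** **Who the assistants are.** The sentence that says they differ by arm stands between one about obtaining and assessing outcomes and one about submitting outcome measurements. Section 3.11 gives delivery to physiotherapists and nurses. The assistants in question are therefore the outcome collectors. Nothing in the Protocol rotates them or crosses them over the arms.

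**Why the arm contrast is affected.** Let D be the systematic difference between two assistants (or two sets of assistants) in the follow-up scores they obtain. Let p_T and p_C be the shares of CBT and control patients seen by the first. Then

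expected arm difference = treatment effect + (p_T − p_C) × D.

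- Arm-specific assistants: p_T = 1 and p_C = 0, so the contrast carries the whole of D.
- Assistants covering both arms, assigned independently of allocation: p_T = p_C in expectation, so the D term drops out.

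Baseline adjustment or change scores do not remove D. Baseline is collected before allocation, so D enters only at follow-up.

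**The plan's own sample size (section 3.5, knee pain).** Inputs: SD 10.85, means 16.54 and 20.68, Z values 1.96 and 0.842.

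- Difference = 20.68 − 16.54 = 4.14; effect size = 4.14 / 10.85 = 0.38.
- n = 2 × (1.96 + 0.842)² / 0.38² = 108.7, which rounds up to 109 per group, as stated. Unrounded inputs give 107.9, or 108.

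**Illustration of size.** The documents give no assistant effect, so the shift b (in SD units, constant across patients, no true treatment effect) is an assumption shown over a range. With n = 109 per group,

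- noncentrality = b × √(n/2) = b × √54.5 = 7.38 × b;
- false-positive rate = Φ(noncentrality − 1.96) + Φ(−noncentrality − 1.96).

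| Assumed b (SD) | Share of planned 0.38 SD | Noncentrality | False-positive rate |
|---|---|---|---|
| 0 | 0% | 0 | 5.0% |
| 0.05 | 13% | 0.369 | about 7% (0.066) |
| 0.1 | 26% | 0.738 | about 11% (0.114) |
| 0.2 | 53% | 1.476 | about 31% (0.315) |

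A larger sample does not help. At 131 per group the rates for 0.1 and 0.2 SD are 12.8% and 36.7%, because the standard error shrinks and the shift does not.

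**The case against.** The strongest reply is that no outcome is scored by an assistant. KOOS, DASS, FABQ, PRSS and PSEQ are completed by the patient, who is openly unmasked. The main risk of biased measurement is thus already disclosed, and restaffing would not change it. What an assistant can influence is prompting, help with items, completeness checks and chasing. This stands, and it is why the effect is probably small.

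Several stronger readings are tempting, and the Protocol does not support them.

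- *The assistants cannot be masked.* The text says that they differ by arm, not that they are told which arm they serve. Unmasking is a likely consequence, not a logical necessity. Disclosure by participants would also remain possible under a shared rota, though then only patient by patient.
- *One assistant equals one arm.* The budget lists two posts and assigns neither to an arm; other staffing over two hospitals is possible. With several assistants per arm, individual differences would partly average out and their spread within an arm could be estimated. Assistants would still be nested in arm, so a systematic difference between the two sets would remain inseparable from treatment.
- *This is the only masking in the trial.* Section 3.8 also describes the hospital staff who contact participants as blinded, and its Procedures part conceals allocation in advance from participants, the recruiting researcher, hospital staff and therapists. These safeguards stand, but they do not cover outcome collection after allocation.
- *The false-positive rates estimate what will happen.* They do not. The shifts are assumed, nothing in the Protocol supports 0.1 or 0.2 SD for self-completed forms, and at 0.05 SD the rate is close to nominal.

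**Conclusion.** The point holds in a limited form. The masking claim and the staffing rule do not fit together as written: the stated masking of outcome collection is unlikely to hold, and the Protocol has no procedure to protect it. Assistant is nested in arm however many assistants there are, so systematic differences between them at follow-up are inseparable from the CBT effect. Neither a larger sample nor baseline adjustment cures this.

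The size is unknown and probably small, because the questionnaires are self-administered. The figures of about 7%, 11% and 31% rest on an assumed constant shift of 0.05, 0.1 or 0.2 SD, no treatment effect, 109 analysed per arm and a normal approximation. They show how the problem grows with the shift, not how large it is. It is worth correcting because the remedy costs little before data collection and the confounding cannot be undone afterwards.

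**What to change.** In section 3.8, delete the sentence that the assistants differ by arm. State instead that each assistant collects outcomes from both arms, that assistants are assigned to patients independently of allocation (for example by hospital), and that they have no access to the allocation list. Assignment by hospital ties assistant to hospital, which is harmless for the arm comparison provided each assistant sees both arms there. Record the assistant ID at each follow-up so that balance over arms can be checked.

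If arm-specific assistants are kept for practical reasons, withdraw the masking statement and report outcome collection as unmasked. That corrects the description but leaves the confounding in place.

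Cost: one or two sentences, a changed rota and one extra data field, with no additional staff.
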